### Encephalography (EEG)

Encephalography (EEG) with video is recommended at the time of TSC diagnosis and as clinically indicated thereafter for surveillance of seizure risk and response to treatment. EEG (60 minutes, included extended epochs of both wake and sleep states) are scheduled to be acquired at every visit, but at minimum will be performed at baseline and at end of treatment (12 months). Sites in this network will utilize identical EEG acquisition protocols and procedures established by the TSC Clinical Research Consortium that are designed to yield comparable results across different equipment platforms. Recordings will utilize 21 gold-plated electrodes placed according to the International 10-20 system with a digital sampling rate at a rate of 2000Hz with no filters, displayed at an effective time scale of 30 mm/sec with 1Hz low frequency and 70Hz high frequency display filters on the left screen, and on the right screen a maximum time scale of 100 mm/sec, 30Hz low frequency filter (high pass) and 100Hz high frequency filter (low pass). These parameters were designed to yield comparable data on Stellate, Nihon-Kohden, XLTEK/Natus EEG systems throughout the consortium. Any additional EEG obtained for clinical purposes between scheduled visits will also be collected for research analysis. The digitized EEG source data will be transferred to CCHMC for central processing and analysis.

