## Secondary Endpoint Analysis and Statistical Considerations:

As described above for primary outcome measures, descriptive statistics will be determined for each composite and individual component measures of the TAND Checklist, VABS, Bayley-4, PLS-5 and ADOS-2 for neurodevelopment and behavior; EEG for electrophysiological connectivity; and dMRI for structural connectivity.

EEG data for conventional analysis (interictal and ictal epileptiform activity) will be sampled at 500 samples/channel/second, 0.5 Hz low pass and 100 Hz high pass filters, and a 60 Hz notch filter, with impedance less than 5 Kohm for all electrodes. Persyst software (San Diego, CA) will be used to digitally view each tracing by a single central reader in the standard timescale of 30 mm/sec and standard filter settings of 1 Hz low-frequency filter (high pass) and 70 Hz high frequency (low pass), along with a 60 Hz notched filter. EEG will be classified according to age-appropriate norms, as either normal or abnormal. Conventional EEG abnormalities will be further evaluated in terms of the presence or absence of background abnormalities, such as generalized or focal slowing, epileptiform discharges (focal, regional, bilateral, or generalized spike or spike and wave discharges), hypsarrhythmia (classic or modified), voltage attenuation, as well as clinical and/or electrographic seizures, in accordance with the NINDS common data element tools for epilepsy. The association between epileptiform discharges and primary efficacy outcome measures will be analyzed using multiple methods, including time-to-event

Version: 7.0\_11May2022

survival analysis, multivariable Cox proportional hazard analysis to assess the contribution of concurrent clinical or genetic variables on the response to treatment, and logistical regression analysis to determine the strength of associations.

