EEG data for quantitative analysis (power, coherence, path length, clustering, and global efficiency) will be imported into Brain Vision Analyzer (BVA) software (Brain Products GmbH) to remove offsets, optimize scaling, and re-reference the data into the desired montage. The power spectral density of the artifact-free bipolar pair EEG data will be calculated using the fast Fourier transform (FFT) function. The 512-point FFT is calculated for artifact-free two-second epochs with a rectangular window, DC de-trending applied to each segment of data, 0.5 Hz overlap at the limits of the band, and yielding a frequency resolution of 0.5Hz. Power will be calculated in six frequency bands, corresponding to delta (0.5-4Hz), theta (4-8Hz), alpha (8-12Hz), beta (12-20Hz), gamma (30-50Hz), ripple frequencies (100-250Hz), and fast ripple frequencies (250-500Hz).

Supplementation of traditional DTI from dMRI data with DCI allows us to characterize changes in free water content, multiple oriented fascicles per voxel, and diffusivity parameters per fascicle, using the concepts of statistical modelling of infinitesimal microenvironments, and the well-established minimum requirements for compartment models. DIAMOND is a finite mixture model of compartments, where the signal arising from each of the compartments is represented by a statistical distribution of 3-dimensional infinitesimal microenvironments. Our model order selection algorithm determines from the dMRI data, exactly the number of compartments that are present at each voxel. DCI enables better delineation of white matter pathways relevant to CNS disease in TSC; allows measurement of the free water volume and improves compensation for partial volume averaging; provides increased sensitivity to detect loss of microstructural integrity; provides intra-voxel orientational heterogeneity and allows tractography of all fascicle orientations; and provides measures of diffusivities from the imaging data.

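### The ripple and fast-ripple EEG bands contain seven harmonics of 60 Hz mains, and section 16.1 specifies no step to remove them; the FFT settings must be reconciled with the bands first

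*Combined protocol and SAP*

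**What the plan says.** All references are to the combined protocol and SAP.

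- **Acquisition** (section 11.6, Encephalography): EEG is recorded "with a digital sampling rate at a rate of 2000Hz with no filters".
- **Conventional reading** (section 16.1, Secondary Endpoint Analysis): "EEG data for conventional analysis (interictal and ictal epileptiform activity) will be sampled at 500 samples/channel/second". Tracings are then viewed with a 70 Hz upper display limit, "along with a 60 Hz notched filter".
- **Quantitative analysis** (same section): the data are imported "to remove offsets, optimize scaling, and re-reference the data into the desired montage". Spectra are computed from bipolar pairs on artifact-free two-second epochs by a 512-point FFT with a rectangular window and DC de-trending, at a stated resolution of 0.5 Hz. No notch, comb or other mains step is named, and no criterion for artifact-free is given.
- **Bands** (same section): "Power will be calculated in six frequency bands", after which seven are listed. The last two are "ripple frequencies (100-250Hz), and fast ripple frequencies (250-500Hz".
- **Endpoints** (section 4.2): the EEG measures named are epileptiform activity, coherence, path length, clustering and global efficiency. Ripple and fast-ripple power are not among them.

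**The concern.** Specifying a 60 Hz notch for conventional reading shows that mains pickup is anticipated. The quantitative path carries no matching step, and a notch at 60 Hz alone would leave the harmonics in place. None of the bands from delta to gamma contains a multiple of 60 Hz, so the gap falls on exactly the two high-frequency bands.

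If harmonics are present, power taken over the whole band adds them to the cerebral signal. A change in electrode contact or equipment between visits could then look like a change in the biomarker. With five infants there is little averaging to absorb this. The plan gives these bands some weight: section 2 says high-frequency oscillations may reflect changes in epileptogenicity, and section 16.1 intends direct biomarker comparison with the vigabatrin prevention trial, where interference could differ in level.

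**Working it through.** **Inputs from the documents:** bands 100-250 and 250-500 Hz; FFT of 512 points; epoch 2 s; resolution 0.5 Hz (all section 16.1, quantitative). Acquisition rate 2000 Hz, unfiltered (section 11.6). Conventional rate 500 Hz and 60 Hz notch (section 16.1, conventional). **Not in the documents:** the amplitude of mains harmonics and of background activity above 100 Hz. Values for these below are assumptions.

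**1. The plan's own resolution.** Sampling rate = points / duration = 512 / 2 = 256 Hz. Resolution = 256 / 512 = 0.5 Hz, so the stated figure reproduces, but only at 256 Hz. The highest frequency available is then 256 / 2 = 128 Hz. That covers 28 of the 150 Hz in the ripple band (19%) and none of the fast-ripple band.

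**2. Which harmonics can enter.** Multiples of 60 Hz within the limits: 120, 180, 240 (three) and 300, 360, 420, 480 (four), seven in all.

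| Sampling rate | Upper limit | 512 points last | 512-point resolution | Points for 2 s | Harmonics below limit |
|---|---|---|---|---|---|
| 256 Hz | 128 Hz | 2 s | 0.5 Hz | 512 | 1 of 7 |
| 500 Hz | 250 Hz | 1.024 s | 0.98 Hz | 1000 | 3 of 7 |
| 2000 Hz | 1000 Hz | 0.256 s | 3.9 Hz | 4000 | 7 of 7 |

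Computing the bands as listed needs at least 1000 Hz (2 × 500), and all seven harmonics are then inside.

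**3. Possible size (assumed amplitudes).** Share of band power from n harmonics = nA² / (nA² + B²), where A is the rms of each harmonic and B the rms of the background in the band. For example, the ripple band with A = 0.5 and B = 1 µV gives 0.75 / 1.75 = 43%.

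| A per harmonic (µV) | Ripple, B = 0.5 / 1 / 2 µV | Fast ripple, B = 0.5 / 1 / 2 µV |
|---|---|---|
| 0 | 0% / 0% / 0% | 0% / 0% / 0% |
| 0.1 | 11% / 3% / 1% | 14% / 4% / 1% |
| 0.5 | 75% / 43% / 16% | 80% / 50% / 20% |
| 1.0 | 92% / 75% / 43% | 94% / 80% / 50% |

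**4. Cost of leaving the harmonic bins out, at 0.5 Hz resolution.** Ripple bins: 150 / 0.5 + 1 = 301. Fast-ripple bins: 250 / 0.5 + 1 = 501. A ±1 Hz exclusion removes 5 bins per harmonic: 3 × 5 = 15 of 301 (5.0%) and 4 × 5 = 20 of 501 (4.0%).

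**5. Whether the exclusion works.** Simulation at 2000 Hz with two-second epochs and a rectangular window, assuming 1 µV rms ripple-band background and 0.5 µV rms per harmonic. Ripple power was 1.00 without mains and 1.75 with it. After exclusion and rescaling it was 1.00 with mains at 60.00 Hz, 1.01 at 60.02 Hz and 1.05 at 60.05 Hz. Recovery in the fast-ripple band was not simulated. Drift there is larger in Hz: 0.05 Hz at the fundamental becomes 8 × 0.05 = 0.4 Hz at 480 Hz.

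**The case against.** **The plan is not without protection.** A reader might infer that the pipeline removes no mains at all. The text does not support that: subtracting within bipolar pairs cancels pickup common to both electrodes, and artifact rejection can drop contaminated epochs. This stands as a limit on the point, but it does not close it. Unequal pickup survives subtraction, and artifact-free is undefined. The only display settings in the documents stop at 70 or 100 Hz, where activity at 120-480 Hz would not be seen; none are given for the quantitative software.

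**The stated FFT cannot reach most of these frequencies.** This is correct, and it is the more basic defect. A 512-point FFT yields 512 / 2 + 1 = 257 bins in all, so the 301 and 501 bins above do not exist under it. At 2000 Hz the same FFT has 3.9 Hz resolution, and a ±1 Hz exclusion is narrower than one bin. This changes the order of the repair but does not remove the need for it: any setting that can deliver the listed bands admits all seven harmonics, and even at 256 Hz the 120 Hz harmonic remains.

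**The consequence is small.** Also largely correct. Ripple power is not a named endpoint in section 4.2, section 16.2 describes a five-infant pilot, the analysis is mainly descriptive, and section 5 specifies one clinical site, which limits variation between rooms and equipment. Further, section 16.1 says power is calculated; that it is summed over every bin in the band is an interpretation.

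**Conclusion.** The gap is real and minor. The plan names two bands that contain seven mains harmonics, uses unfiltered recordings, and specifies no step to remove the harmonics. Ripple and fast-ripple power may therefore partly reflect interference.

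A reader might go further and conclude that these measures do reflect it, or take some part of the percentage table as an estimate. The documents give no amplitudes, and the share runs from 0% to 92% (ripple) or 94% (fast ripple) across the assumed values. It is an unquantified risk, not a demonstrated bias.

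The harmonic count and the conflict between FFT length, epoch and bands follow from the documents by arithmetic. The share of band power and the recovery after exclusion rest on assumed amplitudes. The primary endpoints and the EEG measures named in section 4.2 are not shown to be affected.

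**What to change.** In section 16.1, quantitative EEG:

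1. State the sampling rate used for spectral analysis and make FFT length, epoch and bands agree. At the 2000 Hz acquisition rate, two-second epochs need 2000 × 2 = 4000 points, which keeps the 0.5 Hz resolution and reaches 500 Hz. Correct the band count from six to seven in the same edit.
2. Before computing ripple and fast-ripple power, leave out bins within ±1 Hz of 120, 180, 240, 300, 360, 420 and 480 Hz, or apply an equivalent harmonic line-noise filter. Report power per remaining Hz.
3. Define artifact-free, including the display bandwidth at which epochs are selected.

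The order matters, because the exclusion has no meaning on the 512-point FFT as written. The cost is a few lines in the SAP and the analysis script, 5% of ripple bins and 4% of fast-ripple bins. No new recordings are needed. If mains drift proves appreciable, check the exclusion width at the upper harmonics before fixing it.

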## 16.2 Study Size and Power Calculations

The original study was powered for the planned enrollment of Stage 2, in which 60 subjects were to be randomized 2:1 for treatment with TAVT-18 (sirolimus) vs. placebo. These power calculations remain valid for STOP2B: TSC-STEPS (CCHMC IRB#2021-0438) that has replaced Stage 2 of the current study. However, with enrollment under the current protocol now limited to Stage 1 only (n=5), this study is no longer powered for definitive analysis and becomes a true pilot study aimed at obtaining preliminary data with regard to potential treatment safety concerns and an estimation of patient variability in treatment response. Analyses for statistical significance will still be carried out with the modifications as outlined above, but it is expected that unless the treatment effect size is very large compared to a similarly matched historical cohort from the TACERN/TSC-EBS study, statistical significance will not be achieved with such a low number of treated individuals in this study. Nonetheless, descriptive analysis as a pilot study using sirolimus (TAVT-18) in a patient population (TSC infants 0-12 months of age) that has hereto never previously been studied in a prospective fashion still has immense scientific and clinical value. Furthermore, should the TAVT-18 sirolimus formulation be further developed as a potential clinical treatment for this indication, the descriptive statistics will provide essential data for estimating potential treatment effect size and interpatient variability values that will prove essential for determining study size and study power.

## **17 HUMAN SUBJECT PROTECTION**

Compliance with Good Clinical Practice (GCP) guidelines for the conduct and monitoring of this clinical trial will occur through observation of the ethical and regulatory requirements presented in ICH E6, Good Clinical Practice: Consolidated Guideline. The study (protocol, informed consent, advertisements, subject information sheets and Investigator CV and credentials) should be reviewed and approved by the Institutional Review Board (IRB) or ethics committee. Changes to the protocol will be approved by the IRB. Subjects must sign written informed consent prior to being screened, before undergoing any study procedures.

The investigators and institutions affiliated with this study will permit trial-related monitoring, audits, IRB/IEC review, and regulatory inspection(s) by providing direct access to source documents.

### **17.1 Privacy and Confidentiality**

Subject confidentiality will be maintained by the investigator, the investigator's associates and co-workers, and by all administrators who are part of the project. Confidentiality will be maintained according to ICH E6; 4.8.10, part O: "Records identifying the subject will be kept confidential and, to the extent permitted by the applicable laws and/or regulations, will not be made publicly available. If the results of the trial are published, the subject's identity will remain confidential."

The investigator, his or her staff and associates, and the appropriate regulatory agencies may use the information included in this protocol as necessary for the conduct of the trial and the safety of subjects. The subject/legal guardian may obtain the results of clinical labs, tests and procedures obtained for this research study.

Subjects will be identified only by a unique identifier for research specimens collected and shipped to analysts outside the consortium. Any publications will reflect only unique identifiers. All information related to this study will be kept in secure and locked offices.

Clinical data on paper forms will be stored separate from the patient chart. The data on paper will be kept locked. Any data on computer will be accessible only by password access. Only members of the research team will have access to these files.

## **17.2 Informed Consent Process**

Informed consent is an ongoing process that includes the signing of an informed consent document. Parents/LARs are required to sign an informed consent prior to being screened, and before undergoing any study procedures or assessments, in accordance with International Conference on Harmonisation (ICH) E6; 4.8, "Informed Consent of Trial Subjects." When substantial modifications are made to the informed consent, the DSMB or IRB may require that all subjects currently enrolled in the study will be re-consented; ICH E6; 4.8 guidelines would still apply.

Parents/LARs will be provided with a copy of the informed consent that explains the purpose of the study, the study procedures, and assessments. Parents/LARs will also be provided with the telephone numbers of the investigator and qualified personnel who can assist with their questions and concerns.

The following is the consent process that will be used for this project:

- Subjects are recruited from the patient populations at each participating center.
- A copy of the informed consent is given to the parents/LARs before signing the consent. The content of these documents, and the nature of the study, is discussed with the parents/LARs before obtaining their signature. If there are no questions regarding the studies or the content of the consent forms, the parent and/or guardian is requested to sign the consent in the presence of a member of the investigation team.
- Parents/LARs are given copies of the consent with signatures to keep.

• For advertisements used for recruitment purposes for this study, prior approval will be obtained from the institutional review board (IRB).

### **18 FUNDING SOURCES**

The primary source for funding this clinical trial is the Clack Foundation and private donations in smaller amounts from individual patients and families donating to general TSC research at Cincinnati Children's Hospital. This funding supports the necessary infrastructure and resources necessary for successful completion of the study, including all study visits and procedures for the primary safety, efficacy, developmental/behavioral assessment, and later PK/PD endpoint analyses. Tavanta Therapeutics, Inc. is providing TAVT-18 (sirolimus) drug supply for the entire study and supplemental funding to support study visits and procedures for the initial openlabel, detailed PK analysis portion of the study (Stage 1). The TS Alliance, a national patient advocacy not-for-profit organization, provides funding for tissue and blood biosample acquisition, shipping, processing, and storage at the TSC Biorepository in Grand Rapids, Michigan.

### **19 SUBJECT COMPENSATION**

Subjects will not be compensated for participating in this trial. Limited travel reimbursement for qualifying expenses may be available. Clinical procedures and tests described above that are clinically indicated (meaning they would be done even if the subject was not participating in this study) may be charged to the subject and/or their medical insurance. Examples include but are not limited to EEGs, MRI, laboratory studies, clinical evaluations, and/or additional developmental assessments. However, procedures and tests that would only be done because of participation in this research study, such as measurement of sirolimus levels, will not be charged to the subject and/or their insurance.

#### **20 PUBLICATION PLANS**

Manuscript(s) and abstract(s) prepared from the data collected during this trial will be prepared by the study investigators using standard publication guidelines.

The investigators on the clinical trial will be given the first and exclusive opportunity to analyze, present and publish data collected from their investment of time and effort. It is the obligation of the study investigators to disseminate results and it is expected that the investigators will write manuscripts including study design and primary results as well as other methodology and preplanned analyses of secondary outcomes.

